Exercise and Pharmacotherapy for Anxiety in Cardiac Patients

NCT02516332

**1. Protocol Title:** Exercise and Pharmacotherapy for Anxiety in Cardiac Patients: The UNWIND Study

**2. Purpose of the Study:** Coronary heart disease (CHD) is the leading cause of death in the United States; more than 600,000 Americans suffer a fatal cardiac event each year. Traditional CHD risk factors such as high blood pressure, smoking, and elevated cholesterol do not fully account for the timing and occurrence of CHD events. The term "cardiovascular vulnerable patient" has been used to describe patients susceptible to acute coronary events based upon plaque, blood, or myocardial characteristics. Psychosocial factors also have been shown to be associated with increased adverse health outcomes and increased cardiovascular vulnerability. For example, clinical depression and elevated depressive symptoms are associated with increased morbidity and mortality, and as a result, the American Heart Association has recommended that clinicians should routinely assess depression in CHD patients. Although much research and clinical recommendations have focused on depression, the significance of anxiety has been largely ignored, despite the fact that anxiety disorders are as prevalent as depression in the general population and are associated with similar levels of disability.

Despite the prevalence and prognostic significance of anxiety in CHD populations, there have been few randomized clinical trials (RCTs) specifically targeting anxious CHD patients. Anxiolytic medications, including selective serotonin reuptake inhibitors (SSRIs), have been shown to be effective in treating anxiety. SSRIs have been evaluated for the treatment of clinical depression in cardiac patients, with equivocal results. Surprisingly, to our knowledge, there have been no RCTs examining the efficacy of medications for treating anxiety in CHD patients. Moreover, because many cardiac patients are reluctant to take additional medications and psychotropic medications may not be effective for everyone or may produce unwanted side effects, there continues to be a need to identify alternative approaches for treating anxiety in cardiac patients. We believe that exercise may be one such approach.

The purpose of this study is to evaluate the following hypotheses in a population of CHD patients with elevated symptoms of anxiety. The present study will examine the impact of a 3-month intervention of exercise, Lexapro, or placebo on anxiety symptoms and CHD biomarkers among individuals with cardiac disease and elevated anxiety. We hypothesize the following: (1) Both exercise training and medication will reduce anxiety symptoms to a greater extent than placebo; (2) Exercise training will improve CHD biomarkers of risk including autonomic regulation, vascular endothelial function, and inflammation more than either medication or placebo; and (3) Improvements in CHD biomarkers will be mediated by reductions in symptoms of anxiety. We also will explore potential moderators of treatment (e.g., anxiety diagnoses, CHD severity) as well as the longer-term benefits of treatment by documenting medical events and health care costs over a follow-up period of up to 4 years.

**3. Background & Significance:** Over \$100 billion is spent on CHD each year in direct medical costs, disability payments, and lost productivity.[1] Mental illness also is a major health problem in this country, with estimated direct costs of \$57.5 billion in 2006.[2] Mental disorders are associated with significant impairment of function that may, at times, be worse than that of chronic medical disorders. Anxiety disorders are the most commonly diagnosed forms of mental illness in the U.S. and are responsible for one-third of the total expenditures of the federal government for mental illness.[3] Approximately half of those costs are due to the repeated use of health care services since people with anxiety disorders often solicit medical evaluation for symptoms that resemble physical illnesses.[4] Nationally representative surveys indicate that as many as 30% of patients will suffer from some kind of anxiety disorder during their lifetimes,[5] a figure that has increased significantly over the past 2 decades. Anxiety symptoms have been correlated with the presence of one or more chronic diseases,[6] as well as impaired work performance, increased use of medical services, decreased well-being, and lowered functioning.[7, 8] Although the actual prevalence of anxiety disorders among cardiac patients is not known, Tully and Cosh reported an 11-14% prevalence of generalized anxiety disorder (GAD) across 12 studies (N=3485) and a pooled lifetime prevalence of 26%.[9] Frasure-Smith[10] noted that 5.3% of a sample of 804 patients with stable CHD had GAD and 41.4% had elevated anxiety symptoms measured by the Hospital Anxiety and Depression Scale-Anxiety (HADS-A). Thus, anxiety is common in CHD patients. However, the prior

set of reviews raised questions about the significance of anxiety in CHD patients and of the novelty of exercise to treat anxiety. Our team took up this challenge by revisiting and expanding our previous review of the relevant literature and conducting new analyses of pilot data from our laboratory, both of which proved helpful in further articulating a working conceptual model and providing a rationale for our proposed RCT.

Anxiety and CHD Risk. Findings from a number of prospective epidemiological studies report a strong association of anxiety with mortality in healthy individuals [11-13] and in CHD patients.[10, 14-19] Our own studies have shown that elevated scores on the anxiety subscale of the HADS were associated with increased risk of mortality after accounting for established risk factors in 934 men and women with CHD (Hazard Ratio HR, 2.27; 95% CI, 1.55 to 3.33,  $p < .001$ ).[20] Elevated anxiety symptoms have been shown to be associated with a 2-fold increased risk of mortality in CABG patients[16, 18] and in outpatients with CHD.[10, 21, 22] Frasure-Smith and colleagues reported that CHD patients with GAD assessed two months following hospital discharge showed a 2.3-fold increased risk of adverse cardiac events, and Strik et al.[21] reported a 2.8-fold increased risk of adverse events in acute post-MI patients in which anxiety was measured one month following hospital discharge. Similarly, a 2-fold increased risk of adverse events was observed in stable CHD patients[23] and in patients with elevated anxiety during annual clinic visits.[24] Similar to the depression literature,[25] not all studies have found a prognostic relationship, especially when anxiety was measured in-hospital following an acute coronary event or during diagnostic exercise stress testing.[8, 26-30] In the proposed study, anxiety symptoms will be evaluated outside of the clinic and hospital environment in individuals with stable CHD with high levels of anxiety.

Anxiety and depression share high comorbidity.[10, 31, 32] Findings from several recent prospective studies suggest that anxiety predicts increased risk independently of depression, and that the presence of both anxiety and depression identifies individuals at greater risk of mortality than those with either prognostic factor alone.[20, 33] We observed a 3-fold increased risk of mortality in CHD patients with comorbid anxiety and depression, compared with an approximate 2-fold risk in patients with either anxiety or depression alone.[20] The additive effects of anxiety and depressive symptoms have been noted by other investigators,[33, 34] and we will explore this issue in our proposed trial.

Treatment of Anxiety Disorders in Cardiac Patients. Despite compelling reasons for treating anxiety in CHD patients, there have been few trials that have examined the effects of treating anxiety symptoms in cardiac patients, and no studies reported the effects of treating anxiety on clinical outcomes. Several studies, including the ENRICH trial, have examined the effects of treating depressed post-MI patients,[35] and several pharmacologic studies have examined the effects of SSRIs on depressive symptoms and outcomes in cardiac patients.[36-40] The SADHART-CHF trial found no advantage for sertraline over placebo in either reducing depression or in improving clinical outcomes.[40] The SADHART study[36] also reported no differences between CHD patients receiving sertraline compared to placebo, although greater reductions in depressive symptoms were observed in the subset of patients with more severe depression. We will consider more severe anxiety (i.e., diagnosed anxiety disorders) as a potential moderator of treatment in our proposed RCT.

Exercise and Anxiety. The use of aerobic exercise has been widely used in many secondary prevention programs[41] and may reduce risk of fatal CHD events.[42] The mechanisms for this benefit remain uncertain, although exercise has been shown to reduce traditional risk factors, such as hypertension and hyperlipidemia,[41] attenuate cardiovascular responses to mental stress and reduce myocardial ischemia,[43-46] and reduce depressive symptoms in patients with MDD,[47] heart failure,[48] and in CHD patients with elevated depressive symptoms.[49] Epidemiological studies have observed an inverse relationship between exercise and anxiety. In a study of 8,098 adults, Goodwin[50] reported that persons who indicated that they exercise “regularly” were at reduced risk for being diagnosed with an anxiety disorder compared to their sedentary counterparts. There have been many exercise trials that have reported anxiety as an outcome.

For example, Wipfli and colleagues[51] found that exercise was associated with an overall effect size of 0.48, indicating greater reductions in anxiety symptoms compared to no-treatment controls, and Herring

and colleagues[52] reported that exercise was associated with an overall effect size of .29, compared to control conditions. In a review of 8 RCTs of patients with a broad range of anxiety disorders, Jayakody[53] noted that exercise seems to be effective as an adjunctive treatment for most anxiety disorders, but there were too few studies to provide meaningful conclusions. In response to the prior review, we re-examined the exercise literature and identified only 12 RCTs specifically targeting patients with high anxiety, most of which had serious methodological shortcomings, including small sample sizes, lack of blinding of assessors, confounding of exercise with other treatments, and no adherence to intent-to-treat analytic principles.[54] In one of the few studies of cardiac patients, Lavie and Milani[55] reported more than a 69% reduction in anxiety among highly anxious participants in an exercise-based cardiac rehabilitation (CR) program; however, there was no control group and exercise was only one component of the intervention. In the one RCT that targeted cardiac patients with elevated anxiety, Oldridge and colleagues reported greater reductions in symptoms of anxiety assessed by the STAI and POMS after 8 weeks of CR compared to community care controls.[56, 57] However, the CR group also received concurrent weekly 90-minute group counseling sessions, including training in progressive relaxation, so that the benefits of exercise training could not be determined. Thus, while results from previous exercise studies are encouraging, there remains an important gap in understanding the potential therapeutic benefits of exercise, especially among anxious cardiac patients who are vulnerable to adverse cardiac events.

Biomarkers of CHD Risk. Reliance on "hard" clinical endpoints (MI and death) that occur infrequently and require large sample sizes over extended follow-up intervals has proven to be a major challenge to furthering our understanding of the optimal ways to treat vulnerable cardiac patients because of the obvious logistical and financial obstacles such investigations present. One solution to this problem is to first study intermediate markers of risk in patients who are vulnerable to untoward cardiac events.[58] Examination of changes in intermediate endpoints can provide important insights into the mechanisms and potential value of clinical interventions and has a number of important advantages over "hard endpoints," in that fewer patients are required to detect treatment effects and changes in cardiac risk can be reliably and objectively measured over short follow-up intervals. Following the guidelines advanced by a panel of prominent cardiovascular scientists,[59, 60] we propose to examine intervention effects on autonomic, vascular, and inflammatory biomarkers of cardiovascular risk (i.e., "intermediate endpoints") in "vulnerable" CHD patients with high anxiety:

*Heart rate variability* (HRV) is widely recognized as an important index of autonomic regulation of the heart and prognostic indicator of risk and will serve as our primary biomarker of interest. Reduced 24-hour HRV independently predicts mortality in community samples[61-63] and patients with stable CHD,[64] with a recent MI, [65] or with heart failure (HF).[66]

*Baroreceptor reflex sensitivity* (BRS) is also an index of cardiac regulation by the parasympathetic nervous system (PSNS), with experimental models showing that low levels of BRS predict sudden cardiac death (SCD) due to ventricular fibrillation.[67] Anxiety has been linked to reduced PSNS control of heart rate in several different populations, including patients with anxiety disorders,[68-72] MDD, [73, 74] and CHD,[75] as well as healthy volunteers.[76] Elevated sympathetic nervous system (SNS) activity is another pathophysiological aspect of autonomic dysregulation contributing to the development of CHD[77] that is thought to contribute to increased cardiovascular risk associated with anxiety.[78, 79]

Although no study has compared the effects of an SSRI with exercise training on HRV in anxious cardiac patients, it is well documented that SSRIs that inhibit the reuptake of norepinephrine reduce HRV.[80, 81] Several RCTs have provided evidence that regular exercise improves HRV, as well as BRS, in middle-aged and elderly sedentary subjects[82, 83] and patients with CHD. In the present proposal, 24-hour HRV will be our primary biomarker in examining the impact of exercise and anxiolytic medication on cardiovascular risk in anxious CHD patients, with SNS activity also assessed in order to provide a comprehensive assessment of intervention effects on autonomic regulation.

*Endothelial dysfunction* plays a vital role in the development, progression, and clinical manifestations of atherosclerosis.[84, 85] It can be assessed non-invasively using standardized vascular ultrasound techniques to determine flow-mediated dilatation (FMD) of the brachial artery,[86] has been

[figure not shown]
related to a wide range of CHD risk factors,[87] and has been shown to be prognostic in cardiac patients. Impaired FMD has been linked to elevated depression symptoms in stable CHD patients,[88] and to elevated anxiety symptoms in CHD patients following a percutaneous coronary intervention.[89] Several studies also have shown that acute mental stress is associated with impaired FMD.[90-92] There is preliminary evidence that exercise may improve endothelial function in CHD patients. Several cross-sectional studies have found that self-reported physical activity is associated with preserved endothelial function.[93, 94] Several small interventional studies also have shown that FMD may be improved by exercise training in cardiac patients.[95-98] These observations suggest that reducing anxiety symptoms may result in improved FMD and that anxious CHD patients randomized to the exercise intervention may demonstrate the most marked improvements in FMD.

*Inflammation* is widely considered to play a central role in the development and progression of CHD. C-reactive protein (CRP), an acute-phase reactant primarily produced in hepatocytes, is a highly sensitive marker of underlying systemic inflammation.[99] An elevated level of CRP is an independent risk factor for MI and stroke.[100, 101] Interleukin-6 (IL-6) is an inflammatory cytokine that may be the initial event leading to an increase in CRP levels, and recent meta-analyses indicate that IL-6 may be more strongly related than CRP to the promotion of atherosclerosis.[102, 103] Elevated levels of both CRP and IL-6 have been observed in patients with depression,[104-106] but few studies have examined the relationship with anxiety.[107] In a subsample of healthy participants in the ATTICA study, Pitsavos et al.[108] observed a significant dose-response relationship between the severity of anxiety symptoms and CRP and IL-6. In a cross-sectional study of 120 stable CHD outpatients, Bankier et al.[109] also found GAD to be associated with increased CRP. In a sample of 682 post-ACS patients, Frasure-Smith et al.[110] reported that HRV was correlated with inflammatory markers and suggested that interventions targeting regulation of both autonomic control and inflammation may be especially worthwhile. The interventions proposed in this RCT are designed to accomplish this goal.

Summary. We propose to examine the effects of exercise and anxiolytic medication on both symptoms of anxiety and on "intermediate endpoints" that are associated with adverse outcomes in CHD patients. In this application, we propose a RCT to compare the effects of exercise training and anxiolytic medication (escitalopram, Lexapro) to a placebo in anxious patients with CHD. Patients will be assessed on clinical, behavioral, and physiological dimensions at baseline, 3 months (post-treatment), and 6-month follow-up. Additional measures of quality of life also will be obtained along with annual follow-ups to document clinical events and medical costs. The findings from this RCT will have directly translational implications for anxiety assessment and management in CHD patients.

**4. Design & Procedures:** This study will be a single-site, randomized clinical trial of exercise training and anxiolytic medication in the treatment of anxiety in anxious CHD patients without MDD as a primary diagnosis. One hundred fifty men and women aged  $\geq 40$  years with stable CHD and elevated anxiety symptoms (HADS-A scores  $\geq 11$ ) will be randomly assigned to Exercise Training, Medication (escitalopram), or Placebo. Patients will be evaluated for anxiety at baseline, after 3 months of treatment, and at 6-month and annual follow-ups. Three months is ample time to observe cardiovascular conditioning effects, even among older cardiac patients, whose responses are often quite variable, and is also adequate to assess the efficacy of pharmacologic treatment. Comprehensive assessments will include clinical evaluations of anxiety and measures of intermediate surrogate endpoints, including autonomic, vascular, and blood markers of risk. Following the completion of the 3-month treatment program, subjects will undergo a post-intervention repeat assessment. Patients will then undergo a 6-month follow-up evaluation for anxiety and CHD risk status and will be followed annually for anxiety and

Figure 1

clinical events (see [Figure 1](#)). All assessors will be blinded to patients' treatment group assignment; groups receiving a pill will be double-blind. Following completion of the intervention, participants will be advised to contact their referring physicians, if necessary, for further treatment, or they will be referred to appropriate mental health care providers.

### **I. Assessment of Anxiety**

Patients will undergo a comprehensive assessment of anxiety. The primary outcome measure will be scores on the Hospital Anxiety and Depression Scale – Anxiety (HADS-A). The HADS-A is a commonly used psychiatric self-report questionnaire designed to identify anxiety and depression among patients in nonpsychiatric medical settings, and has been shown to detect independent constructs of anxiety and depression. It has excellent psychometric properties, and has been widely used in outpatient RCTs in patients with clinical anxiety. Published clinical cutoffs are 0-7 (normal), 8-10 (mild), 11-14 (moderate), and 15-21 (severe). Our eligibility criteria will include patients with HADS-A scores  $\geq 8$ , which represents a more conservative cut-point for identifying patients with significant anxiety who are at increased risk for adverse CHD events and who may receive greater benefit from treatment.

A clinical psychologist will administer modules from the Structured Clinical Interview for DSM-5 Disorders (SCID), including the anxiety disorder section, the mood disorder section (to rule out primary MDD), the somatization section, and the alcohol abuse and/or dependence section. The psychologist also will administer the 14-item Hamilton Anxiety Rating Scale (HAMA) to obtain a clinical rating of anxiety symptom severity.

Other psychiatric self-report anxiety assessments will include the Anxiety and Depression Detector (ADD), the Patient Health Questionnaire 9 item (PHQ-9), the Anxiety Sensitivity Index (ASI), and the General Anxiety Disorder 7-item questionnaire (GAD-7). Together, these assessments will afford a comprehensive analysis of a patient's severity of anxiety symptoms and the comorbidity with depression. The ADD provides 5 items that effectively and efficiently screen for panic disorder, PTSD, social phobia, GAD, and depression. The PHQ-9 is a brief, reliable, and valid measure of depression severity. The ASI assesses fear of arousal-related sensations, and we will be using the test to assess physical factors of arousal. The GAD-7 is an efficient screening tool for assessing GAD severity.

The 20-item Trait section of the Spielberger Stait-Trait Inventory (STAI) also will be presented to the patients to assess anxiety symptoms before treatment. However, to assess ongoing treatment response, participants will complete the 20-item State section of the STAI at weekly intervals throughout the duration of the 3-month intervention by a clinician who will be blinded to patients' treatment group status. The STAI will be used to evaluate the process of change and to assess at-risk patients (i.e., worsening anxiety) regularly and systematically. Suicidal potential also will be carefully assessed. Contact time will be documented and content limited (to avoid simulating psychotherapy, which would seriously confound data interpretation).

Importantly, patients with primary MDD will be excluded from this trial. However, because symptoms of depression are likely to co-occur with anxiety, we also will assess depressive symptoms with the Beck Depression Inventory-II (BDI-II). The BDI-II is a widely used measure of depressive symptomatology, consisting of 21 items, each corresponding to a specific category of symptoms and attitudes. It has been shown to be both a reliable and valid measure of depression severity and has been used in many major interventional trials of cardiac patients. Item #9 (suicidality) of the BDI-II will be used to assess suicidal ideation and administered weekly along with the STAI.

Electronic-based questionnaires (e-questionnaires) will be used for all assessments, both anxiety and quality of life, except for interview-based assessments. These e-questionnaires will be delivered during participants' visits to Duke for pre- and post-intervention assessments. A Duke Psychiatry computer will be used and secured by Psychiatry Computer Support. The computer log-in will be performed and documented by study personnel; the computer will be used only for the survey purpose;

the study personnel will remain in the room with the participants while they have computer access; and study personnel will document log-off before leaving the room. The computer will be setup such that only necessary software will be installed on the computer, and access to other applications and network assets will be limited. The software necessary for assessments is Qualtrics, a Duke-approved survey platform.

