## **12. Data Management and Statistical Considerations**

**Data Analytic Approach.** The basic analytic strategy is a linear model carried out in the MPlus modeling software,[164] with treatment group contrasts as factors, and ethnicity, age, gender, and pre-treatment measure of the outcome variable as the adjustment covariables. The intent-to-treat principle (ITT) will be followed in all models, using full information maximum likelihood available in MPlus to manage missing data. For the case of the primary outcome, HADS-A, the model will include post-treatment HADS-A score as the response, with the predictors including two planned contrast variables representing 1) the two active treatments (exercise and escitalopram) vs. placebo and 2) exercise vs. escitalopram, with ethnicity, gender, age, and pre-treatment level of the HADS-A as the adjustment covariables. The contrast tests among treatment groups will be examined directly, i.e., no omnibus or “gateway” test will be required before interpreting them. In support of the HADS-A outcome, we also will compare the pattern of weekly changes in the STAI scores over time using a repeated measures model with Proc Mixed in SAS (SAS Institute, Cary, NC). The primary biomarker outcome, HRV, will be evaluated similarly. It is possible that a small number of participants may require off-protocol psychotropic medication during the course of the trial. These participants will be included in the ITT analysis and will not be replaced. We also will perform a sensitivity analysis with change in medication included as an adjustment variable in the statistical model. Finally, we will compare the treatments on the number of clinical events using a generalized linear model with the appropriate distributional form (e.g., negative binomial), using the same contrasts and covariates as in the linear model described above.

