**Power Analysis.** Our study is powered with a focus on the primary hypothesis test: the treatment effect on anxiety as measured by HADS-A scores. We estimated power and sample size under the following assumptions: an alpha of .05, a linear model with age, gender, ethnicity, and baseline HADS-A score as covariates, a conservative estimate of the R-squared of .20 for the full model predicting post-treatment HADS-A, a 15% attrition rate, and two planned contrasts: active treatment vs. placebo and exercise vs. escitalopram. The comparison of primary interest will be active treatments vs. placebo. We estimate that a sample size of 150 (127 after attrition) will yield .80 power to detect at least a .45 SD difference between the active treatments and Placebo. In the general linear model, the exercise vs. escitalopram test will be only slightly less powered in being able to detect a .50 SD difference. In response to a previous reviewer comment, we believe that achieving this effect size is feasible. For example, in individuals with high anxiety sensitivity, Broman-Fulks[167] reported a .61 SD difference between exercisers and controls. We also re-examined data from a subset of highly anxious patients ( $STAI \geq 45$ ;  $N=32$ ) participating in our recently completed UPBEAT study[49] and found an effect size of .85 SDs on the STAI for both active treatments vs. placebo controls. We note that our power estimates are conservative in that the R-squared for the model is likely to be greater than .20 and dropout may be lower than 15%. With respect to the secondary outcome of HRV, our prior work showed that the R-squared between the baseline covariates and HRV was .73, greatly increasing the power of the tests of treatment on HRV. For the test of exercise vs. escitalopram on HRV, our primary CHD biomarker of interest, we will have a power of .80 to detect a .25 SD effect at alpha of .05. Finally, for our ancillary outcomes, including FMD, lipids, urinary catecholamines, and inflammatory markers, we have sufficient pilot data for FMD, which we use as an exemplar for power estimates: our earlier work showed that for FMD, the multiple R-squared between the baseline covariates (age, gender, ethnicity, and baseline FMD) and FMD was .50. Thus, we will have a power of .80 to detect a .34 SD effect for FMD with an alpha of .05. We estimate the power for the secondary analysis of treatment on time-to-clinical-event, assuming an event rate of 50% in the placebo group (based on unpublished data from our prior work[49]), 42 months for patient accrual, median follow-up time of 30 months and alpha = .05, is .80 to detect a reduction in event rate of 50% between both treatment groups and placebo, as well as .80 to detect a reduction in event rate of 56% between either intervention group individually and placebo. Unpublished data from our recently completed ENHANCED trial[168] revealed a 54% reduction in major adverse cardiac events among patients participating in CR compared to a matched control group of patients who did not participate in exercise-based CR.

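### The primary HADS-A model leaves out baseline STAI-Trait, which is already collected; adding it as a pre-specified covariate could give a small gain in precision at almost no cost

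*Combined protocol and SAP*

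**What the plan says.** Section 4, I. Assessment of Anxiety, makes HADS-A the primary outcome and also uses it for entry: "Our eligibility criteria will include patients with HADS-A scores" at or above 8. Inclusion criteria (Section 5) repeat 8, while the opening of Section 4 gives 11. Those statements need to be reconciled, but the point made here does not depend on which applies.

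The same subsection says of the 20-item Trait section of the STAI: "STAI) also will be presented to the patients to assess anxiety symptoms before treatment". Section 9 (Randomization) places allocation after the assessments, so the score is a true baseline value.

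Section 12, Data Analytic Approach, regresses post-treatment HADS-A on two treatment contrasts, "with ethnicity, gender, age, and pre-treatment level of the HADS-A as the adjustment covariables". No other anxiety score enters. The STAI scores used in that section are the weekly ones, in a separate supportive repeated-measures model. Baseline STAI-Trait is not mentioned.

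The Power Analysis uses the same covariates and "a conservative estimate of the R-squared of .20 for the full model predicting post-treatment HADS-A". It adds that "our power estimates are conservative in that the R-squared for the model is likely to be greater than .20".

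**The concern.** The main comparison, both active arms against placebo, rests on about 25 placebo completers (30 x .85 = 25.5). With so small an arm, a baseline variable that predicts the 3-month score is a cheap source of precision. STAI-Trait measures the same broad construct as the outcome, is taken before allocation and is already on file. If it carries information about post-treatment HADS-A beyond what baseline HADS-A carries, omitting it leaves the confidence interval for the main contrast wider than it need be. Only precision is at stake. Bias and Type I error are not affected.

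**Working it through.** **1. The plan's own figure.** Inputs from Section 12: "an alpha of .05, a linear model with age, gender, ethnicity, and baseline HADS-A score as covariates"; R-squared .20; 15% attrition (150 to 127). Allocation from Section 9 is 60:60:30, so 127 completers split about 101.6 to 25.4. A two-sided test is assumed.

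- SE = sqrt(1 - .20) x sqrt(1/25.4 + 1/101.6) = .894 x .222 = .198 SD.
- .45/.198 = 2.27, and 2.27 - 1.96 = .31, so power is about .62.

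The plan states "sample size of 150 (127 after attrition) will yield .80 power to detect at least a .45 SD difference between the active treatments and Placebo". That figure does not reproduce with the planned allocation; 127 split equally gives .81. The second contrast does reproduce (.50 SD, 50.8 per arm: power .80). So the starting point here is about .61 to .62, not .80.

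**2. What decides the gain.** Write X for baseline HADS-A, S for baseline STAI-Trait and Y for post-treatment HADS-A. Adding S to a model that contains X cuts residual variance by the squared partial correlation of S and Y given X:

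pr = (r_SY - r_XY x r_XS) / sqrt[(1 - r_XY^2)(1 - r_XS^2)].

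The documents give none of these correlations. Assumed before selection: r_XY = .66, r_XS = .60 to .75, r_SY = .50 to .60.

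- Best corner (.60, .60): (.600 - .396)/sqrt(.5644 x .6400) = .204/.601 = .339; squared, .115.
- Worst corner (.75, .50): (.500 - .495)/sqrt(.5644 x .4375) = .005/.497 = .010; squared, .0001.

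**3. Effect of the entry cut.** Selecting on X alone leaves the distribution of S and Y given X unchanged, so under a linear, constant-variance model pr is unchanged as well. As illustration, suppose entry keeps the top 41.4%. That is the share with elevated HADS-A quoted in Section 3; the cut behind it is not given. The variance of X falls to v = .319 of its unselected value, and R-squared with X alone is

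.4356v/(.4356v + .5644) = .139/.703 = .197,

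which matches the plan's .20. If 20% or 60% are kept instead (v = .219, .422), R-squared with X alone is .144 or .246. The proportional cut from adding S in the best corner is 11.5% in all three cases.

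**4. Power at .45 SD, 102 against 25.5.** Non-central t with ncp = .45 x sqrt(102 x 25.5/127.5)/sqrt(1 - R-squared) = 2.03/sqrt(1 - R-squared). Without STAI-Trait, R-squared is .197 and power is .614.

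| r_XS | r_SY | Cut in residual variance | R-squared with S | Power |
|---|---|---|---|---|
| .60 | .60 | 11.5% | .290 | .667 |
| .60 | .50 | 3.0% | .221 | .627 |
| .75 | .60 | 4.5% | .233 | .634 |
| .75 | .50 | 0.0% | .198 | .614 |

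The best corner narrows the confidence interval by about 6% (sqrt(.885) = .941) and is worth about 17 patients (127.5/.885 - 127.5 = 16.6).

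**5. Cost.** One of about 120 residual degrees of freedom. Break-even is a gain in R-squared of about .80/120 = .007. In the worst corner the addition is therefore a net loss of about 0.8% (1/120) in variance.

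**The case against.** The strongest reply is that nothing here is wrong. Adjusting for the baseline of the outcome with age, gender and ethnicity is a standard pre-specified model, and which further scores to add is a matter of judgement. The gain rests wholly on assumed correlations and may be nil. Nothing in the documents favours STAI-Trait over HAM-A or GAD-7. All of this stands. Choosing one score in advance is still better than leaving the choice open. Anxiety-disorder status, balanced at randomisation but absent from the covariate list, is a separate question.

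Three stronger readings are tempting and are not supported:

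- A reader might infer that the HADS-A entry cut creates the loss, because it truncates the one anxiety covariate. Truncation does lower the R-squared from HADS-A, but by step 3 the proportional gain from STAI-Trait is the same at any cut.
- A reader might take the R-squared of .20 as evidence that HADS-A predicts poorly. The plan presents it as a deliberately cautious value for the whole model and expects a higher one.
- A reader might expect the covariate to repair the shortfall from .80 power. It reaches at most about .67 here; R-squared of about .48 would be needed. That shortfall comes from the 4:1 split and is a separate issue.

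**Conclusion.** The omission is confirmed: baseline STAI-Trait is collected before randomisation, is absent from the primary model and is named in no analysis. The planned analysis of covariance remains valid and unbiased. What may be forgone is between 0% and about 12% of residual variance, or power of .61 to .67 in place of about .61. That range depends on assumed correlations, on joint normality with constant residual variance, and on a two-sided .05 test with 15% attrition. This is a small improvement at almost no cost, not a defect that threatens the trial's conclusion.

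**What to change.** In Section 12, Data Analytic Approach, before unblinding, add baseline STAI-Trait to the covariates of the primary HADS-A model, next to pre-treatment HADS-A, ethnicity, gender and age. State that it is the only added anxiety score, which rules out a later choice among scales, and say how a missing baseline value is handled so that every randomised patient stays in the model. The cost is one line of text and one degree of freedom; no new data are needed. Do not raise the power claim on the strength of this change.
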